#### 5.6.5. Supportive Care Measures

Supportive care measures including blood products, infection prophylaxis and growth factors will be administered according to standard practice at the investigational site (See Recommendations in [Table 9](#)[Table 9](#)).

Formatted: C-Hyperlink

**Table 9: Recommendations for the use of concomitant medications and therapies**

Category of Use	Medication	Comment on Use	Restriction on Use
Recommended	Prophylactic antibiotics, antifungal agents, and antiviral agents	Strongly encouraged	Refer to Appendix Table 22 Table 22 , Table 23 Table 23 , Table 25 Table 25 for restrictions, and Section 5.3.
	Antiemetic agents	According to standard of care at the site	Avoid QTc prolonging antiemetics (Section 10)
Allowed	Oral allopurinol or rasburicase	According to standard of care at the site	None
	Leukapheresis	According to standard of care at the site	Before first dose on Day 1 = 1 only
	Red blood cell transfusion	None	None
	Platelet transfusion	None	None
	White blood cell transfusion	At Investigators discretion according to standard of care at the site	None
	Myeloid growth factors or platelet growth factor	At Investigators discretion according to standard of care at the site	None
	Erythropoietin or darbepoetin	At Investigators discretion according to standard of care at the site	None
	Any other medication for supportive care	At Investigators discretion according to standard of care at the site	None

Consistent with subject safety and comfort, administration of any prescription or over-the-counter drug products other than study medication should be minimized during the study period. Subjects should be discouraged from use of street drugs, herbal remedies, self-prescribed drugs, tobacco products, or excessive alcohol during the clinical study.

If considered necessary for the subject's wellbeing, drugs for concomitant medical conditions or for symptom management may be given at the discretion of the investigator. The investigator's decision to authorize the use of any drug other than study drug should take into account subject safety, the medical need, the potential for drug interactions, the possibility for masking symptoms of a more significant underlying event, and whether use of the drug will compromise the outcome or integrity of the study.

Subjects should be instructed about the importance of the need to inform the clinic staff of the use of any drugs or remedies (whether prescribed, over-the- counter, or illicit) before and during the study.

Recommendations for specific types of concomitant therapies, supportive care; diet and other interventions are as follows:

- Infections secondary to myelosuppression are common in subjects with AML, and may be related to underlying disease, chemotherapy, or both. Therefore, the use of prophylactic antibiotics, antifungal agents, and antiviral agents is recommended according to institutional standards. The use of strong CYP3A inhibitors is not allowed. Therefore, the use of antifungal, antiviral and antibiotics agents listed in Appendix [Table 29](#)[Table 29](#) are prohibited until DDI assessments based on DDI sub-study have been conducted to fully characterize the risk.
- All ongoing medications and therapies (including herbal products, nutritional supplements, and nontraditional medications) at screening will be considered prior medications. All prior medications (within 30 days of enrollment) and concomitant medications will be recorded in the case report form.
- If a prohibited medication is inadvertently administered/ taken by the subject, the subject may remain on study as long as the prohibited medication is discontinued as soon as feasible. If a prohibited medication is considered essential for the subject well-being, continuation on study with concomitant administration of such medication(s) will need to be discussed with and approved by the principal investigator and sponsor.

Formatted: C-Hyperlink

## **6. DOSING DELAYS / MODIFICATIONS / DISCONTINUATIONS FOR POSSIBLY RELATED ADVERSE EVENTS**

### **6.1. Toxicity At Least Possibly Related to Study Drugs**

Subjects experiencing unacceptable toxicity at least possibly related to the study drugs should temporarily stop treatment according to the guidelines in the dose adjustment schema.

### **6.2. Toxicity Grading**

Toxicity grading will be according to the NCI CTCAE, v5.0. To prevent unnecessary morbidity, the following guidelines for dose adjustment for toxicities at least possibly related to study drugs are recommended.

### 6.2.1. Dose Adjustments for Hematological Adverse Events (AE) Considered at Least Possibly Related to Study Drugs

Dose reduction/interruption/discontinuation decisions should be based on the CTCAE version 5.0 and the guidelines provided below.

Subjects with acute leukemias usually present with abnormal peripheral blood counts at the time therapy is started, and myelosuppression is an expected event during the course of therapy for acute leukemia. Thus, subsequent courses may be administered regardless of peripheral blood counts during the first 3 cycles and/or in the presence of residual leukemia. After Cycle 3, treatment interruptions and dose adjustments may be considered according to the following guidelines when there is no evidence of active leukemia:

- Subjects with a response (no evidence of any residual leukemia on bone marrow and/or peripheral blood by morphology or flow-cytometry) will have dose modifications for hematological toxicities as specified in the azacitidine and venetoclax PIs and in Section [5.4.15.4.1.1](#) and Section [5.4.2](#). See [Table 10](#) for recommended dose modifications for DS-1594b for hematologic adverse events that are considered at least possibly related (see Section [5.1](#) for preliminary dose levels).
- If there are persistent peripheral blood blasts, or the bone marrow shows  $\geq 5\%$  blasts or any evidence of residual leukemia by morphology or flow, treatment may be continued regardless of neutrophil and platelet count with supportive care as needed. Dose-interruptions of individual drugs in these subjects should be considered on an individual case-by-case basis and discussed with the PI and sponsors.
- Investigators should, whenever possible, determine which medication is causing the toxicity and interrupt or dose reduce, as applicable.

Formatted: C-Hyperlink

**Table 10: DS-1594b Dose Adjustments for Neutropenia At Least Possibly Related to Study Drug**

Grade	Occurrence	Dose Modification
1 or 2	Any	No modification
3 (without infection or febrile neutropenia)	Any	No modification
$\geq 3$ (with infection or febrile neutropenia) or 4	1 st	Interrupt dosing until resolution to $\leq$ Grade 2 or baseline 

If recovery occurs <math>\leq 14</math> days of holding DS-1594b: resume dosing at the same dose level the subject was on at the time of the interruption

If recovery occurs <math>> 14</math> days of holding DS-1594b: resume dosing at one dose level lower than the dose level the subject was on at the time of the interruption (Dose level -1)

Grade	Occurrence	Dose Modification
	2 nd	
Interrupt dosing until resolution to <math>\leq</math> Grade 2 or baseline
 
 
• If recovery occurs <math>\leq</math> 14 days of holding DS-1594b: resume dosing at the same dose level the subject was on at the time of the interruption
 
• If recovery occurs <math>></math> 14 days of holding DS-1594b: resume dosing at one dose level lower than the dose level the subject was on at the time of the interruption (Dose level -1 or -2, depending on the dose level the subject was on at the time of the interruption)
 

	3 rd	
 
• If the subject is on Dose level -2 at the time of the event, permanently discontinue therapy.
 
• If the subject is not on Dose level -2 at the time of the event, interrupt the dosing until resolution to <math>\leq</math> Grade 2 or baseline and resume dosing at one dose level lower than the dose level the subject was on at the time of the interruption (Dose level -1 or -2, depending on the dose level the subject was on at the time of the interruption).
 

	4 th	
 
• Permanently discontinue therapy.
 

Note: Treatment interruptions and dose modifications other than the ones mentioned above can be considered after discussion with the PI and proper documentation of the rationale.

#### 6.2.2. Dose Adjustments for Non-Hematologic AEs Considered at Least Possibly Attributable to Study Drugs

Investigators should, whenever possible, determine which medication is causing the toxicity and interrupt or dose reduce azacitidine, venetoclax, and/or interrupt DS-1594b, see

[Table 11](#)

Formatted: C-Hyperlink

**Dose reductions of azacitidine will be as follows:** Baseline dose level: 75 mg/m^2 x 7 days, dose level -1 of azacitidine: 50 mg/m^2 x 7 days, dose level -2: 37.5 mg/m^2 x 7 days, dose level -3: 25 mg/m^2 x 7 days. Further reductions or modifications to schedule beyond what is shown above or alternative reductions (e.g. 75mg/m^2 x 5 days) may be allowed if deemed in the subject's best interest by the treating physician after approval from the PI and Sponsors.

**Dose reductions of venetoclax will be as follows:** Baseline dose level of venetoclax: 400mg, dose level -1 of venetoclax: 200mg, dose level -2: 100mg, dose level -3, 50mg. Alternatively, the duration of venetoclax administration can be decreased (e.g. decrease from 28-days per cycle to 21-days per cycle to 14-day per cycle to 10 days per cycle) rather the dose being reduced.

**Dose reductions for DS-1594b** will be allowed if warranted by Investigator and after discussion and approval by PI and Sponsors and will follow the Phase 1 doses used for DS-1594b

[\(Table 6\)](#)

Formatted: C-Hyperlink

**Table 11: Dose Adjustments of Azacitidine, Venetoclax, and/or DS-1594b for Non-Hematologic Possibly Related AEs, Clinically Significant in the Opinion of the Investigator**

Grade	Occurrence	Dose modification
1 or 2	Any time	No dose reduction
3 (Persistent Grade 2: Consider similar dose adjustments if persistent and not responding to optimal management in the opinion of PI and treating physician)	1st and 2nd time	Hold suspected drug. -Resume the held drug at prior dose if recovery to $\leq$ Grade 1 occurs within 14 days. -If toxicity persists for 15-28 days, hold the drug and resume at prior dose if recovery to $\leq$ Grade 1 OR resume the drug at ONE dose level below current dose if recovery to $\leq$ Grade 2. -If toxicity persists for $>28$ days, hold the drug; resume the drug at ONE dose level below current dose if recovery to $\leq$ Grade 2.  Dose re-escalation to prior dose of the drug is permitted in accordance with the dose-escalation guidelines in Section 5.
	3rd.	Hold suspected drug. Follow until toxicity $\leq$ Grade 2. Resume the held drug at ONE dose level below current dose. Dose re-escalation of the drug to prior dose is permitted in accordance with the dose-escalation guidelines outlined below Subjects who are experiencing ongoing dose delays $>8$ weeks due to unresolved grade $\geq 3$ adverse events should be taken off treatment.
	4th time	Discontinue therapy
4	Any time	Discontinue therapy

Note: For dose adjustments to DS-1594b for QTc Interval Prolongation or Acute Differentiation Syndrome, refer to [Table 12](#)[Table 12](#) and [Table 13](#)[Table 13](#).

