#### **5.5.4. Suggested Standard Dose Reductions/Modifications/Discontinuations:**

- Vincristine 1 mg IV Days 1 and 11 (50% reduction) if:
  - Bilirubin  $> 2$  mg/dl and  $\leq 3$  mg/dl
  - Clinically significant grade 2 peripheral neuropathy persisting greater than 2 weeks.
  - Eliminate vincristine for Grade 3-4 peripheral neuropathy, including Grade 3-4 ileus suspected to be related to vincristine, or bilirubin  $> 3$  mg/dL.
- Methotrexate:
  - Consider reduction by 25% to 50% for Grade 3 or worse mucositis with previous methotrexate course.
  - Reduce by 50% for calculated creatinine clearance 10-50 mL/min, if  $< 10$  mL/min, hold methotrexate.
  - Reduce by 25% to 75% for delayed excretion and/or nephrotoxicity with previous methotrexate course.
  - Reduce by 50% for pleural effusion or ascites (drain effusion if possible).
- **Non-hematological toxicity**

- If Grade 3 or 4 non-hematologic toxicity is at least possibly attributable to DS-1594b, dose interruption of DS-1594b is required. Subjects who experience drug-related Grade 3 non-hematological toxicity may be given a subsequent course one dose level below the previous course, but the subject must have recovered to Grade  $\leq 1$  before start of the next course. If a subject has drug-related Grade 4 non-hematological toxicity, he/she may receive a subsequent courses at one reduced dose level after resolution of toxicity to Grade  $\leq 1$ , only if approved by the PI based on the clinical significance of the toxicity and only if subject has had derived a benefit from the therapy. The dose of DS-1594b can be decreased during a cycle, at the discretion of treating physician and PI, for chronic Grade 2 non-hematological toxicity. Other dose modifications may be considered as clinically indicated with documentation and approval of the PI.

- **Hematologic toxicity**

- Dose interruptions or modifications will be made for Grade 4 hematological toxicities, only if considered at least possibly related to DS-1594b and not related to underlying disease or the use of chemotherapy, as determined by the treating physician and the study PI. Subjects with baseline neutropenia or those who have significant bone marrow involvement may be particularly at high risk.

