### 5.5.5. Maintenance

Maintenance chemotherapy with vincristine, DS-1594b, and prednisone for approximately 24 months beginning at Dose level 0 or lower dose level if prior toxicity required dose reduction of agents (titrate to keep ANC  $> 0.5 \times 10^9/L$  and platelet count  $\geq 30 \times 10^9/L$ ) (See [Table 8](#)[Table 8](#) below):

- Vincristine 2 mg IV on Day 1 approximately every 28 days.
- Prednisone 50 mg orally daily on Days 1 to 5 approximately every 28 days with vincristine.
- DS-1594b continuously, twice daily (or daily) every 28 days at the same dose received during induction/consolidation.
- For DS-1594b dose adjustments, see Section 6.
- Suggested maintenance chemotherapy dose adjustments are in [Table 8](#)[Table 8](#) below.

Formatted: C-Hyperlink

Formatted: C-Hyperlink

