#### 6.2.3.2. Combined Elevations of Aminotransferases and Bilirubin

Combined elevations of aminotransferases and bilirubin, either serious or non-serious and whether or not causally related, meeting the laboratory criteria of a potential Hy's Law case [ALT or AST  $\geq 3 \times$  ULN with simultaneous TBL  $\geq 2 \times$  ULN] should always be recorded as an AE or SAE within 24 hours of awareness, with the investigator's assessment of seriousness, causality, and a detailed narrative.

Regarding the detailed narrative(s):

- Serious AESI: The narrative will be captured directly in the EDC system.
- Non-Serious AESI: The narrative will be captured on a form outside of the EDC system (paper form).

For liver elevation, workup elevations meeting FDA DILI criteria below:

Elevation of liver enzymes that meet the criteria below should be investigated and the cause identified when possible:

- ALT  $>8 \times$  ULN; or
- AST or ALT  $>5 \times$  ULN for more than two weeks; or
- ALT or AST  $>3 \times$  ULN, but not reaching the limits in the above criteria, in combination with clinical symptoms suggestive of hepatitis; or
- ALT or AST  $>3 \times$  ULN with TBL  $>2 \times$  ULN.

Once the cause of liver enzyme elevation is identified, remove or treat the contributing cause.

If the above criteria are met and the elevation is considered to be related or possibly related to DS-1594b, dosing should be interrupted.

Liver enzyme level testing will be repeated at least weekly, or more frequently, based on degree of hepatic laboratory abnormality. If the liver enzyme levels return to baseline levels, DS-1594b may be resumed at ONE dose level below the current dose level. If toxicity does not improve/resolve within 28 days, then DS-1594b will be discontinued. Upon resumption of DS-1594b, if liver enzyme elevations recur, treatment must be permanently discontinued.

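### Table 11 and Section 6.2.3.2 give conflicting DS-1594b instructions for the same related liver-enzyme event, and Table 11 also differs from Section 5.5.4 in Cohort D, with no order of precedence stated

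*Combined protocol and SAP*

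**What the plan says.** **Table 11 (Section 6.2.2)** covers possibly related, clinically significant non-haematologic events for azacitidine, venetoclax and/or DS-1594b. At Grade 3, first and second time, the suspected drug is held, then: "Resume the held drug at prior dose if recovery to" Grade 1 or lower occurs within 14 days. For 15 to 28 days the prior dose is still allowed at Grade 1 or lower, or one level less at Grade 2 or lower. Beyond 28 "days, hold the drug; resume the drug at ONE dose level below current dose if recovery to" Grade 2 or lower. At the third occurrence: "Resume the held drug at ONE dose level below current dose". Therapy ends at the fourth occurrence, or at any Grade 4 event. The third-occurrence row also takes subjects off treatment for delays over 8 weeks from unresolved Grade 3 or higher events. The note beneath reads "Note: For dose adjustments to DS-1594b for QTc Interval Prolongation or Acute Differentiation Syndrome, refer to" Tables 12 and 13.

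**Section 6.2.3.2** lists four liver criteria, including ALT above 8 x ULN alone and AST or ALT above 5 x ULN for more than two weeks. If a qualifying elevation is related or possibly related, DS-1594b is interrupted. Then: "If the liver enzyme levels return to baseline levels, DS-1594b may be resumed at ONE dose level below the current dose level". Failure to improve or resolve in 28 days leads to discontinuation. Finally: "Upon resumption of DS-1594b, if liver enzyme elevations recur, treatment must be permanently discontinued".

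**Section 5.5.4 (Cohort D)** allows a further course one level lower after drug-related Grade 3 toxicity has recovered to Grade 1 or lower. After Grade 4, "he/she may receive a subsequent courses at one reduced dose level after resolution of toxicity to Grade" 1 or lower, subject to PI approval and benefit from therapy. Section 5.5.5, on Cohort D maintenance, adds: "For DS-1594b dose adjustments, see Section 6".

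**The concern.** Hepatotoxicity is one of the study's two categories of adverse event of special interest, and this is the first clinical study of DS-1594b. If two sections answer the same event differently, then restart dose, recovery threshold and permanent stopping depend on which section is consulted. Exposure and discontinuation data would then mix two policies.

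There may also be a statistical consequence. Section 3.2.2 includes a line that refers to events leading to a lower dose or to stopping therapy. If that line is a DLT criterion in its own right, the choice of dosing rule can feed into the DLT count, which drives the BOIN decisions, the Cohort C and D safety run-ins and the Phase 2 toxicity boundary.

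**Working it through.** **1. Do both rules reach the same event?** Yes. Both apply to events at least possibly related to DS-1594b. Despite its heading, Section 6.2.3.2 covers isolated transaminase rises as well as combined elevations.

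**2. Liver event, side by side.**

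| Point | Table 11 | Section 6.2.3.2 |
|---|---|---|
| Recovery needed | Grade 1 or lower for prior dose; Grade 2 or lower for one level down | Baseline |
| Restart dose, Grade 3, 1st and 2nd time | Prior dose if Grade 1 or lower by day 28 | One level lower |
| Past day 28 | Restart one level lower at Grade 2 or lower | Discontinue if not improved/resolved |
| Second event | Handled as the first | Permanent discontinuation |
| Third event | Restart one level lower | Not reached |
| Fourth event | Discontinue | Not reached |
| Grade 4 | Discontinue | Resumption one level lower possible |

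Neither rule is uniformly stricter: Section 6.2.3.2 is stricter at Grade 3, Table 11 at Grade 4. One branch agrees on the dose step: 15 to 28 days with recovery only to Grade 2 gives one level lower in Table 11, although Section 6.2.3.2 would still wait for baseline.

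**3. Is precedence stated?** No. The Table 11 note names two exceptions and liver events are not among them. Sections 6.7 and 6.8 allow departures after discussion with the PI, but do not say which default is being departed from.

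**4. Cohort D.** After Grade 3, Section 5.5.4 gives one level lower; Table 11 allows the prior dose. After Grade 4, Section 5.5.4 allows continuation with approval; Table 11 discontinues. Table 11 names DS-1594b and sets no cohort limit.

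**5. DLT consequence, conditional on the Section 3.2.2 line standing alone.** Grade 4 AST/ALT, Grade 3 AST/ALT for at least 7 days, and Grade 3 with a Grade 2 bilirubin increase are DLTs whichever dosing rule is used. The rule followed matters for events outside those lines, for example a Grade 3 rise above 8 x ULN lasting under 7 days without a Grade 2 bilirubin rise. A rise above 5 x ULN for more than two weeks cannot be that short; if Grade 3 throughout, it is a DLT anyway.

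Effect of one reclassified event:

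- *Phase 1, Table 4.* The boundaries reproduce as 0.157 and 0.238 (target 0.2; alternatives 0.6 x 0.2 = 0.12 and 1.4 x 0.2 = 0.28). 0/3 = 0 is at or below 0.157: escalate. 1/3 = 0.333 exceeds 0.238: de-escalate, or three more subjects if the SRC so decides.
- *Safety run-in, Section 3.3.* 1/6 is considered safe; 2/6 is not.
- *Phase 2, Table 22.* Stop if Pr(P_T > 0.2 | data) > 0.85 with a beta(0.5, 0.5) prior, that is, 1 - F(0.2; 0.5 + x, 0.5 + n - x), where F is the beta distribution function. The boundaries reproduce as 4/10, 5/15, 6/20 and 8/26. For n = 10: x = 3, beta(3.5, 7.5), gives 0.795 (continue); x = 4, beta(4.5, 6.5), gives 0.934 (stop).

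Table 24 also reproduces: looks at 10, 15 and 20 with a maximum of 26 give an early-stop probability of 0.2509 at a true DLT rate of 0.2. For scale only, an assumed shift in the apparent rate from 0.20 to 0.25 or 0.30 would move that probability from 0.251 to 0.444 or 0.636. Nothing in the documents says that reclassification would be this frequent.

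**The case against.** The strongest reply is that the specific rule governs the general one, and that neither side is rigid. Section 5.5.4 is headed as suggestions, the Section 6.2 guidelines are recommendations, and DS-1594b reductions under Section 6.2.2 need PI and sponsor approval. This softens the conflict in practice. It does not settle it: Table 11 names its exceptions and omits liver events, and Section 6.2.3.2 makes stopping at recurrence mandatory.

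On Cohort D, the cross-reference to Section 6 sits under Maintenance, and the Section 6.2.2 text points DS-1594b reductions to Table 6, the Cohort C dose table. One could read Section 5.5.4 as governing the chemotherapy courses and Section 6 as governing maintenance. That reading is coherent, but it is not stated, and Table 11 is not confined to Cohort C. The Cohort D conflict is therefore real but secondary.

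A reader might infer more than the text supports:

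- *Full-dose re-challenge three times under Table 11.* The prior dose is available at most twice; the third restart is one level lower, and there is an 8-week delay limit.
- *Flatly opposite action at day 28.* Section 6.2.3.2 stops only if there is no improvement or resolution, and Table 11 restarts only after improvement to Grade 2 or lower. A subject who has improved by day 28 does not clearly trigger the stop.
- *DLT status generally depending on the section used.* Only a subset of liver events is affected, and the Section 3.2.2 line directly follows the QTcF line, so it may not stand alone.
- *182 subjects, or 32 in Cohort D, affected.* Those are enrolment ceilings (66 + 2 x 26 + 2 x 32 = 182), not counts of qualifying events.

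**Conclusion.** The conflict between Table 11 and Section 6.2.3.2 is in the current text. At Grade 3 the two differ on recovery threshold, restart dose and action at recurrence, and partly on the day-28 action; at Grade 4 they differ on whether treatment may resume at all. No passage says which prevails. The Cohort D difference between Table 11 and Section 5.5.4 also stands, as a lesser point.

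The DLT consequence is conditional. It assumes that the Section 3.2.2 line is a stand-alone criterion, that the event is not already a DLT by grade or duration, that it is graded 3 (the documents do not reproduce the CTCAE cut-offs), and arguably that the lower-dose restart falls within the 28-day window. Under those assumptions one event can change a Phase 1, run-in or Phase 2 decision. How often this would happen cannot be derived from the documents. No sample size, boundary or stated operating characteristic is wrong because of this point.

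**What to change.** Reconcile Table 11, Section 6.2.3.2 and Section 5.5.4 so that one DS-1594b instruction applies per event and cohort, and state the order of precedence in the Table 11 note. For Cohort D, say which section governs the chemotherapy courses and which governs maintenance. In Section 3.2.2, clarify whether the line on dose reduction or discontinuation is a DLT criterion in its own right or belongs to the QTcF line above it.

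The sponsor and the SRC should decide which rule applies before the note is drafted. Simply adding exceptions in favour of Sections 6.2.3.2 and 5.5.4 would make that clinical choice by default.

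The cost is an amended table note, alignment of the affected sections and one clarified line in the DLT definition. No subjects or procedures are added, and no stopping boundary changes.
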